5.8 Premature Termination or Suspension of Study

This study may be temporarily suspended or prematurely terminated if there is sufficient reasonable cause. Written notification, documenting the reason for study suspension or termination, will be provided by the suspending or terminating party to [name] JDS Therapeutics, NYU medical center, and regulatory authorities. If the study is prematurely terminated or suspended, the PI will promptly inform the IRB and will provide the reason(s) for the termination or suspension.

Circumstances that may warrant termination or suspension include, but are not limited to:

- Determination of unexpected, significant, or unacceptable risk to participants
- Demonstration of efficacy that would warrant stopping
- Insufficient compliance to protocol requirements
- Data that are not sufficiently complete and/or evaluable
- Determination of futility

Study may resume once concerns about safety, protocol compliance, data quality are addressed and satisfy the sponsor, IRB and/or FDA.

6 Study Agent (Study drug, device, biologic, vaccine etc.) and/or Procedural Intervention

6.1 Study Agent(s) and Control Description

The study agent is the HLA vaginal insert, Revaree (brand name). It is a FDA-approved class II medical device. It is a 2g insert that contains 5mg of HLA sodium salt and a base of semi-synthetic glycerides. The off-label use of this device for GSM is considered non-significant risk (NSR) as it does not meet the criteria for significant risk device set forth in 21 CFR 812.3(m). This device is approved as a personal lubricant for vaginal application. This device does not pose significant risk because as mentioned earlier, multiple international trials have shown no side

CONFIDENTIAL

This material is the property of the NYU School of Medicine and Langone Medical Center. Do not disclose or use except as authorized in writing by the study sponsor
Interventional Template Version: 11 January 2019

effects and the only adverse event noted that required treatment was one episode of vulvovaginal candidiasis (10).

The control agent is vaginal estradiol cream, Estrace (brand name). It is a cream composed of 100mcg estradiol in a non-liquefying 1g base containing purified water, propylene glycol, stearyl alcohol, white ceresin wax, mono- and di-glycerides, hypromellose 2208 (4000 cps), sodium lauryl sulfate, methylparaben, edetate di-sodium and tertiary-butylhydroquinone. It is FDA approved for GSM treatment.

6.1.1 Acquisition

Both study agents will be acquired and shipped to [name] office by JDS Therapeutics.

6.1.2 Formulation, Appearance, Packaging, and Labeling

The study agent, Revaree, is manufactured by JDS Therapeutics. It is a semi-solid, off-white suppository for the vagina. The suppository must be removed from its packaging by pulling two pre-cut flyers of the plastic strip. This is a commercially marketed medical 'device,' available for human use in the form, route, and dose planned in this trial.

The control agent, Estrace, is manufactured by Allergan. It is a white cream that must be squeezed onto a calibrated applicator to dose it. This is a commercially marketed medication, available for human use in the form, route, and dose planned in this trial.

6.1.3 Product Storage and Stability

Revaree should be stored at 39°F to 77°F, avoiding void heat over 86°F. Estrace should be stored at 68°F to 77°F with excursions permitted to 59°F to 86°F.

6.1.4 Preparation

No preparation of the study agents is needed.

6.1.5 Dosing and Administration

The study agent, Revaree, has only one dose. As per the manufacturer, the suppository should be placed in the vagina at bed time. It should be removed from the packaging before insertion, inserted into the vagina while laying down with knees bent, and then pushed further into the vagina gently, as far as tolerated. It should be placed twice weekly.

The control agent, Estrace, is dosed by the amount of cream applied to the vagina. The patient will need to attach the applicator to the tube and squeeze the cream into the calibrated applicator accordingly before application at bed time. The dosing will be 100mcg of estradiol (1g of cream) inserted into the vagina twice a week. This dosing is consistent with the manufacturer recommended maintenance dosing for Estrace and it mimics the usage pattern of the other study agent, HLA. Additionally, a study of a similar vaginal cream, Premarin, showed that twice weekly dosing was as efficacious and safe as using the cream daily for 21 days and 7 days off for GSM symptoms (22).

CONFIDENTIAL

This material is the property of the NYU School of Medicine and Langone Medical Center. Do not disclose or use except as authorized in writing by the study sponsor
Interventional Template Version: 11 January 2019

6.1.6 Route of Administration

Vaginal for both study agents.

6.1.7 Starting Dose and Dose Escalation Schedule

The starting doses are mentioned above. There will be no escalation.

6.1.8 Dose Adjustments/Modifications/Delays

There will be no dose adjustments for the study agent, Revaree. It is not physically possible with this formulation of the drug.

Dose modification for the vaginal estrogen cream, Estrace, may occur if a patient exhibits side effects. If a patient starts to exhibit the most common side effects of breast pain, vaginal spotting, or headache, the dose may be decreased or the treatment may be discontinued depending on the clinical context. If there is any concern for an AE, the treatment may be discontinued. If the patient is responding positively to treatment, the dosing will not be increased.

6.1.9 Duration of Therapy

The duration of therapy will be 12 weeks. This is based on evidence that vaginal estrogen therapy can take up to six weeks to offer symptomatic relief in some patients (16). Additionally, with four weeks of usage, vaginal administration of HLA has shown to have significant impact on GSM symptoms.

6.1.10 Tracking of Dose

Subject diary will be used to track date/time of dosing of vaginal estrogen or HLA insert.

6.1.11 Device Specific Considerations

N/A

6.2 Study Agent Accountability Procedures

NYU Investigational pharmacy will be used to ensure the drug and device are stored and dispensed in a regulated manner through the faculty group practice study site. Unused product will be returned to JDS Therapeutics ([name]). Both medications will be stored at the office in a locked cabinet. There will be no additional interventions.

Regular study drug reconciliation will be performed to document drug assigned, drug consumed, and drug remaining. This reconciliation will be logged on the drug reconciliation form, and signed and dated by the study team.

7 Study Procedures and Schedule

7.1 Study Procedures/Evaluations

7.1.1 Study Specific Procedures

- Medical history: will be obtained by interview
 - Included: genitourinary symptoms
- Medication history:

CONFIDENTIAL

This material is the property of the NYU School of Medicine and Langone Medical Center. Do not disclose or use except as authorized in writing by the study sponsor
Interventional Template Version: 11 January 2019

- All history of HRT use currently or in the past
 - Any usage of HRT in the last six weeks would prohibit participation until six weeks off HRT
- Physical Exam:
 - Pelvic:
 - Vaginal pH sample
 - Vaginal tissue sample via scraping for VMI
- VSQ, FSFI, VSI
- Counseling on usage of medication depending on the study arm randomization
- Patient report of medication compliance at twelve week follow-up

7.1.2 Standard of Care Study Procedures

- Demographic information
- Medical history: will be obtained by interview
 - Included: obstetrical, gynecologic, medical, and surgical history
- Medication history:
 - All current medications (prescription and over the counter) usage and dosages
- Physical Exam:
 - Vitals: blood pressure, heart rate, respiratory rate, temperature, height, weight
 - Cardiovascular exam: lung and heart auscultation
 - Abdominal exam: skin, surgical scars, distention, tenderness
 - Pelvic:
 - Speculum: external genitalia and urethral opening, vulva, vaginal, cervix
- Bimanual: cervical os, uterine size (if present), adnexal fullness, adnexal tenderness

7.2 Laboratory Procedures/Evaluations

N/A

7.2.1 Clinical Laboratory Evaluations

- After enrollment
 - Vaginal pH test: will be checked at office at visit one and two
 - Vaginal scraping for microscopy analysis for VMI: will be checked at the office at visit one and two
 - Urine analysis: dipstick urinalysis, including protein, hemoglobin and glucose; if dipstick is abnormal, complete urinalysis with microscopic evaluation is required.

7.2.2 Screening

There will be no screening visit separate from the enrollment visit.

7.2.3 Enrollment/Baseline

Screening/Enrollment/Baseline Visit (Visit 1, Day 0)

- Obtain informed consent of potential participant verified by signature on study informed consent form
- Obtain demographic information, history of present illness, medical history, surgical history, obstetrical history, gynecologic history, medication history, HRT usage history
- Perform physical exam: vitals, cardiovascular, abdominal, pelvic
- Diagnose GSM
- If GSM diagnosis, explain study and verify inclusion and exclusion criteria
- Obtain urine pregnancy test: result must be negative and available prior to administration of study agents

CONFIDENTIAL

This material is the property of the NYU School of Medicine and Langone Medical Center. Do not disclose or use except as authorized in writing by the study sponsor
Interventional Template Version: 11 January 2019

- Obtain urine analysis: result must be negative and available prior to administration of study agents
- Record VAS scores for dyspareunia, itching, and dryness
- Record rugal fold analysis
- Collect pelvic samples for vaginal pH and vaginal tissue scraping for VMI
- Have patient fill out VSQ, FSFI, VSI
- Perform randomization and determine patient study arm
- Give patient appropriate prescription (HLA vs vaginal estrogen)
- Counsel on medication dosage, usage, and application
- Counsel on communication routes to inform research team about side effects and/or AE

7.2.4 Final Study Visit

Final Study Visit (Visit 2, Week 12 +/- 3 to 5 days)

- Record AE as reported by participant or observed by investigator
- Record participant's adherence to treatment regimen
- Record VAS scores for dyspareunia, itching, and dryness
- Record vital signs, results of physical exam including pelvic
- Collect pelvic samples for vaginal pH and vaginal tissue scraping for VMI
- Have patient fill out VSQ, FSFI, VSI, PGI-I
- Discuss the preliminary changes in their symptoms, if any exist
- Provide contact information for [name] to communicate any AE or side-effect experienced after the end of the study if patient believes it is related to the study

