Reactions reported in randomized controlled trials of vaginal estrogen include application site reaction, vaginal bleeding/spotting, breast changes/pain, abdominal bloating/cramps, nausea/vomiting, cervical secretion changes, headache/migraine, fluid retention, elevated blood pressure, mood changes, candidiasis, glucose intolerance, weight changes, libido changes, contact lens intolerance, vision changes, rash, melasma/choasma, hair loss and hirsutism. Despite this risk profile, vaginal estrogen is well tolerated in most patients and is the recommended treatment if first-line over-the-counter vaginal moisturizers and lubricants do not work.

Regarding the office visit, the only potential risk of vaginal tissue sampling may be minimal bleeding, for which local pressure will be applied. If a patient is on oral HRT within 6 weeks of the study, she will not be able to participate in this study.

CONFIDENTIAL

This material is the property of the NYU School of Medicine and Langone Medical Center. Do not disclose or use except as authorized in writing by the study sponsor
Interventional Template Version: 11 January 2019

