4.2 Study Endpoints

4.2.1 Primary Study Endpoints

The primary endpoint will be the change in the VSQ score, between the baseline visit and 12 week follow-up.

The VSQ is a 21-question survey developed in 2012 that specifically asks about GSM symptoms, their emotional impact, sexual impact, and life impact. Among 120 post-menopausal women, this questionnaire was found to have reliability and internal consistency (15). Most importantly, in the absence of a gold standard instrument to assess the quality of life impact of

CONFIDENTIAL

This material is the property of the NYU School of Medicine and Langone Medical Center. Do not disclose or use except as authorized in writing by the study sponsor
Interventional Template Version: 11 January 2019

GSM, this questionnaire is critical. It is more nuanced and disease-specific than VAS scoring, and thus far, an underutilized tool to understand the significant psychological impact of this disease. Because GSM is a symptom-driven disease and patients will likely adhere to a treatment plan if they perceive symptomatic improvement, this study's primary endpoint of treatment success will be measured by improvement in VSQ scoring.

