27. National Research Council. The prevention and treatment of missing data in clinical trials. National Academies Press, 2010.

CONFIDENTIAL

This material is the property of the NYU School of Medicine and Langone Medical Center. Do not disclose or use except as authorized in writing by the study sponsor
Interventional Template Version: 11 January 2019

19 Attachments

19a The Vulvovaginal Symptom Questionnaire

The Vulvovaginal Symptom Questionnaire

The following questions were developed to assess skin symptoms of women. The skin surrounding the vagina is called the vulva. Just like skin in other parts of the body, the vulva can sometimes become irritated. Many women experience discomfort in the region of the vulva. These symptoms may be mild, but can sometimes be severe. The following questions will ask you about your vulvar skin symptoms during the past week.

During the past week, have you been bothered by:

1. Your vulva itching? No Yes
2. Your vulva burning or stinging? No Yes
3. Your vulva hurting? No Yes
4. Your vulva being irritated? No Yes
5. Your vulva being dry? No Yes
6. Discharge from your vulva or vagina? No Yes
7. Odor from your vulva or vagina? No Yes
8. Worry about your vulvar symptoms?
(for example, that it will spread, get worse, scar, etc.) No Yes
9. The appearance of your vulva? No Yes
10. Frustration about your vulvar symptoms? No Yes
11. Embarrassment about your vulvar symptoms? No Yes
12. The effects of your vulvar symptoms on your interactions with others? No Yes
13. The effects of your vulvar symptoms on your desire to be with people? No Yes
14. Your vulvar symptoms making it hard to show affection? No Yes
15. The effects of your vulvar symptoms on your daily activities? No Yes
16. Your vulvar symptoms affecting your desire to be intimate? No Yes
17. Are you currently sexually active with a partner?
 No → Thank you. You are done with this questionnaire.
 Yes → Please proceed with the next 4 questions
18. The effects of your vulvar symptoms on your sexual relationships? No Yes
19. Your vulvar symptoms causing pain during sexual activity? No Yes
20. Your vulvar symptoms causing dryness during sexual activity? No Yes
21. Your vulvar symptoms causing bleeding during sexual activity? No Yes

CONFIDENTIAL

This material is the property of the NYU School of Medicine and Langone Medical Center. Do not disclose or use except as authorized in writing by the study sponsor
Interventional Template Version: 11 January 2019

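### The visit lists place the self-completed VSQ, the primary endpoint, after pelvic procedures and staff questioning, and no text requires it earlier

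*Combined protocol and SAP*

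**What the plan says.** Section 4.2.1 sets the endpoint: "The primary endpoint will be the change in the VSQ score, between the baseline visit and 12 week follow-up". Section 10.4.1 scores each yes as one point, for a range of 0 to 21.

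Visit 1 (Section 7.2.3) opens with consent and history, then "Perform physical exam: vitals, cardiovascular, abdominal, pelvic", then the GSM diagnosis, the study explanation, urine tests, VAS, rugal folds and pelvic sampling. Only then comes "Have patient fill out VSQ, FSFI, VSI", followed directly by "Perform randomization and determine patient study arm".

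Visit 2 (Section 7.2.4) lists adverse events, adherence, VAS and the physical exam, then "Collect pelvic samples for vaginal pH and vaginal tissue scraping for VMI", then "Have patient fill out VSQ, FSFI, VSI, PGI-I". Discussion of symptom changes comes after that. The branch of Section 7.2.5 for women with 12 weeks of use also puts the VSQ after the questioning, exam and sampling.

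The questionnaire in Attachment 19a asks "During the past week, have you been bothered by", followed by items on itching, burning, hurting, irritation and dryness, and later on worry, appearance, frustration and embarrassment. Section 2.4.1 says "the only potential risk of vaginal tissue sampling may be minimal bleeding". Section 10.6.1 acknowledges that an unmasked trial may bias symptom reports, but does not mention the order of assessments.

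**The concern.** A patient-reported primary endpoint is best collected before anyone has examined the woman or talked with her about her condition. Read as a rough sequence, these lists do the opposite at both visits. Two routes of influence are possible. One is physical: an exam and scraping of atrophic tissue shortly before yes/no questions about vulvar discomfort. The other is conversational: at Visit 1 a diagnosis and a study explanation, and at Visit 2 questions on side effects and adherence from staff who know the arm. The second route is the more troublesome, because its content differs between the visits and, at Visit 2, could differ between the arms. The estimates are meant to inform a larger trial (Sections 2.1 and 10.2), and a systematic shift does not shrink with more patients.

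**Working it through.** **Step 1. Compare the lists.** What is listed before the VSQ:

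| Item | Visit 1 (7.2.3) | Visit 2 (7.2.4) | 12-week branch (7.2.5) |
|---|---|---|---|
| Pelvic exam | yes | yes | yes |
| pH sample and scraping | yes | yes | yes |
| GSM diagnosis, study explanation | yes | no | no |
| Adverse-event and adherence questions | no | yes | yes |
| Arm already known | no | yes | yes |
| Discussion of symptom changes | not listed | no, listed after | no, listed after |

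**Step 2. Are the lists a sequence?** No text says so. In 7.2.3 signed consent precedes the study explanation, which cannot be literal. Section 20 is grouped by type of activity: it puts consent below the pelvic exam, and the VSQ below the exam but above pH and VMI. On the other hand, randomization follows the baseline measures and the symptom discussion follows the Visit 2 VSQ, so a rough order is visible. If it is not an order, then timing is uncontrolled. VAS shows that it can vary: it is listed after the pelvic exam at Visit 1 and before it at Visit 2.

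**Step 3. What cancels?** Let B and W be the scores free of any order effect, e1 and e2 the exam effects at the two visits, d the effect of diagnosis and explanation (Visit 1 only), and q the effect of staff questioning (Visit 2 only).

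- Observed change = (W + e2 + q) − (B + e1 + d) = (W − B) + (e2 − e1) + q − d.
- If e1 = e2, the exam term is zero.
- d stays in each arm's change. It arises before randomization, so it is the same in expectation in both arms and drops out of the arm difference.
- q stays in each arm's change. It drops out of the arm difference only if it is equal in both arms, which open-label questioning does not ensure.

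The Protocol Summary puts the emphasis on improvement within the HLA group, which is where both d and q remain.

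**Step 4. Scale.** The plan's precision figure (Section 10.5) is a 95% CI width of 1.7 with at least 80% probability, for 30 per arm and SD 2. I assume that this SD, given for an undefined VLM, is that of the VSQ.

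- One arm's mean: width at the assumed SD = 2 × 2.045 × 2/√30 = 1.49, and P(width ≤ 1.7) = 0.87. The plan's figure reproduces.
- Difference between arms: width = 2.07, and P(width ≤ 1.7) = 0.03. So 1.7 describes a single arm's mean only.
- Half-widths: 1.7/2 = 0.85 for an arm mean; 2.07/2 = 1.03 for the difference.

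Shift in an arm mean = share of women with one item switched × 1 point. The documents give no switch rate, so the range is assumed: 0.2 × 1 = 0.2 and 0.5 × 1 = 0.5. Against 0.85 these are 24% and 59%. If the switching occurs in one arm only, they are about a fifth and about a half of 1.03.

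**The case against.** The strongest reply is that staff may hand out the VSQ first without breaching anything, so this is an unspecified order and not a wrong one. That stands, and it limits the point to a clarification.

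The exam route is also weak. The items ask about the past week, few of them could respond to an exam minutes earlier, and the one bleeding item concerns sexual activity. The same exam precedes the VSQ at both visits and in both arms. One can argue that untreated tissue reacts more, so that e1 exceeds e2 and improvement is overstated. That is plausible, but the documents do not show it.

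Each woman has known for 12 weeks whether she used an insert or a cream, so reordering leaves the main open-label bias in place. This stands too. The adverse-event and adherence bullets are worded alike for both arms, but that does not make the conversations alike.

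A reader might infer more than the documents support:
- *That the baseline VSQ also follows an open-label interview.* It does not; randomization is listed after it.
- *That the plan intends the VSQ to be taken before the exam and departs from its own intent.* No text states such an intent.
- *That the investigator comments on findings before the Visit 2 VSQ.* None of the lists says so, and the discussion of symptom changes comes after it.

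**Conclusion.** The point holds as a minor one. The lists put the self-completed primary endpoint after pelvic procedures at both visits, after diagnosis and study explanation at Visit 1, and after questioning by staff who know the arm at Visit 2. No text requires it earlier. A common exam effect would largely cancel; influences present at one visit only would remain in the change score, and the Visit 2 questioning matters most. This assumes that staff roughly follow the listed order.

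The true size is unknown. The 0.2 to 0.5 points illustrate scale under assumed switch rates and are not an estimate of bias. The sample size and the stated precision are unaffected.

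**What to change.** - **7.2.3:** state that the woman completes the VSQ, FSFI and VSI directly after consent, before history-taking, exam and sampling.
- **7.2.4 and the 12-week branch of 7.2.5:** state that the questionnaires listed there (with PGI-I in 7.2.4) are completed first, before adverse-event and adherence questions, exam and sampling.
- **Section 20:** add a matching note. Reordering the rows would not help, because the table is grouped by type of activity.

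This fits Section 13.3.2, which requires consent before study-specific procedures. The explanation given during consent will still precede the baseline VSQ, so the change removes the diagnosis and exam from that position but not all discussion of the study.

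Cost: a few sentences, with no added procedure, visit or patient. Some women later found ineligible will have completed baseline questionnaires.

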7.2.5 Withdrawal/Early Termination Visit

If 12 weeks of study agent usage:

- Record AE as reported by participant or observed by investigator
- Record participant's adherence to treatment regimen
- Obtain GSM symptom history, and record VAS scores for dyspareunia, itching, and dryness
- Record vital signs, results of physical exam including pelvic
- Collect pelvic samples for vaginal pH and vaginal tissue scraping for vaginal maturation index
- Have patient fill out VSQ
- Discuss the obvious, preliminary changes in their symptoms, if any exist
- Provide contact information for [name] to communicate any AE or side-effect experienced after the end of the study if patient believes it is related to the study

If <12 weeks of study agent usage:

- Record AE as reported by participant or observed by investigator
- Record participant's adherence to treatment regimen
- Record vital signs, results of physical exam including pelvic
- Provide contact information for [name] to communicate any AE or side-effect experienced after the end of the study if patient believes it is related to the study

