5.7.2 Handling of Participant Withdrawals or Termination

Patients who withdraw or terminate participation in this study will be called and a follow-up office visit will be set up at 12 weeks regardless of their participation. If the patient refuses to come in, a phone call will be made to discuss adverse events or unanticipated problems over the phone. If a patient is lost to follow-up, two phone calls to the patient and subsequently two phone calls to next-of-kin will be made in an attempt to reach the patient. There is low concern for long-term and short-term safety with either study agent, particularly for the duration of eight weeks only.

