7.2.6 Unscheduled Visit

- Obtain patient's reason for visit
- Perform relevant physical exam
- Based on the clinical context, determine whether study agent should be continued or discontinued or modified
- Discuss plan with patient
- Based on the clinical context, document whether patient will continue in study or be removed

CONFIDENTIAL

This material is the property of the NYU School of Medicine and Langone Medical Center. Do not disclose or use except as authorized in writing by the study sponsor
Interventional Template Version: 11 January 2019

Concomitant Medications, Treatments, and Procedures

All concomitant prescription medications taken during study participation will be recorded on the case report forms (CRFs). For this protocol, a prescription medication is defined as a medication that can be prescribed only by a properly authorized/licensed clinician. Medications to be reported in the CRF are concomitant prescription medications, over-the-counter medications and non-prescription medications.

Prohibited Medications, Treatments, and Procedures

Treatment with systemic HRT will not be permitted during or within 6 weeks of starting this study.

Participant Access to Study Agent at Study Closure

HLA is an over the counter medication so patients will have access to the study agent after closure. However, the cost will not be covered after study closure and will be the subject's responsibility, so purchasing the study agent may be cost prohibitive.

8 Assessment of Safety

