10.1 Statistical and Analytical Plans (SAP)

As the study is a pilot randomized trial, the results are expected to inform the overall protocol design for a larger effectiveness evaluation, including the statistical analysis plan. Our overall strategy will be to estimate the primary and secondary outcomes for those randomized to HLA, along with the contemporary cohort randomized to vaginal estrogen. Formal comparisons between randomized groups are not of focus, but we will estimate treatment effects along with measures of variability in these measures (95% CI).

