10.3 Analysis Datasets

The analysis dataset will include the intent to treat cohort, to include all those randomized to treatment, as well as a per protocol set to include who used either the control or investigational product for at least 12 weeks.

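### The protocol does not settle whether women who leave before 12 weeks of product use are asked for the week-12 VSQ, so the primary outcome is not assured for them

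*Combined protocol and SAP*

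**What the plan says.** Four places bear on a woman who withdraws or is terminated before completing 12 weeks of product.

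- **Section 5.7.2** says that "a follow-up office visit will be set up at 12 weeks regardless of their participation". It does not list what is assessed there. If she will not attend, "a phone call will be made to discuss adverse events or unanticipated problems over the phone"; no questionnaire is mentioned.
- **Section 7.2.4** (Visit 2, week 12) includes "Have patient fill out VSQ, FSFI, VSI, PGI-I", with no condition on product use. The Schedule of Events also marks the VSQ at Visit 2. It has no column for withdrawal.
- **Section 7.2.5** divides the withdrawal visit by length of use. The list for 12 weeks of use contains the VSQ. The list headed "If <12 weeks of study agent usage" contains adverse events, adherence, vital signs, physical exam and contact information. The VSQ, VAS, pH and VMI are not in it.
- **Section 7.2.6** has the clinician at an unscheduled visit "document whether patient will continue in study or be removed". A woman who stops product but stays in the study still reaches Visit 2, so she is not affected.

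On analysis, section 10.3 defines the "intent to treat cohort, to include all those randomized to treatment". Section 10.4 fits a linear mixed model that takes an absent week-12 value as missing at random. Section 10.1 says the strategy is to "estimate the primary and secondary outcomes for those randomized to HLA", alongside the estrogen cohort.

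**The concern.** Product is given for 12 weeks (6.1.9), so almost every early leaver falls under the shorter list in 7.2.5, the one without the primary outcome. The VSQ is scheduled only at baseline and week 12. A woman without the second score therefore adds nothing to the model beyond her baseline, and missing at random carries the whole inference for her.

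That assumption is weak here because missingness would follow stopping product. In justifying the endpoint, section 4.2.1 says "patients will likely adhere to a treatment plan if they perceive symptomatic improvement". If so, women who leave may well have done worse than their baseline predicts, and the week-12 mean would look too favourable. Section 10.4 names no sensitivity analysis for this.

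The one-arm estimate is exposed most. An equal bias in both arms cancels in their difference but not in the HLA arm mean, which is the plan's stated focus. Section 10.5 notes that no earlier treatment study has used the VSQ, so these estimates will feed directly into the larger trial.

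**Working it through.** **The passages side by side**

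| Route for a woman who leaves early | Week-12 VSQ? |
|---|---|
| 5.7.2 visit run as Visit 2 (7.2.4, Schedule of Events) | Yes |
| 5.7.2 visit run to the under-12-weeks list in 7.2.5 | No |
| 5.7.2 phone call after refusing the visit | Not named |
| Lost to follow-up | No |

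Nothing in the protocol chooses between the first two rows.

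**Inputs from the documents**

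- 60 enrolled, 40 evaluable, 33% combined drop-out, withdrawal, cross-over and missing data (5.6, 10.5).
- 30 per arm, SD 2, 95% CI width of 1.7 with at least 80% probability (10.5). The SD is given for a measure called VLM, which I take to mean the VSQ.
- VSQ scored 0 to 21, one point per yes, so lower is better (10.4.1).

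**The plan's own figures**

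- Enrolment: 40 / (1 − 0.33) = 59.7, rounded up to 60. Reproduced.
- Precision: for one arm mean with n = 30 and SD 2, the probability that the t-based 95% CI is no wider than 1.7 is 0.87, and the width achieved with 80% probability is 1.64. Reproduced as a within-arm figure.
- With 20 women in the arm, that probability falls to 0.32 and the 80% width rises to 2.10.

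**Bias in one arm mean**

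The documents do not say how far unobserved women depart from what their baseline predicts. I assume they are 1 to 3 points worse at week 12.

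Bias = share unobserved × shortfall not explained by baseline

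| Unobserved | Calculation | Bias (points, arm looks better) |
|---|---|---|
| 5 of 60 | 5/60 × (1 to 3) | 0.08 to 0.25 |
| 10 of 60 | 10/60 × (1 to 3) | 0.17 to 0.50 |
| 20 of 60 | 20/60 × (1 to 3) | 0.33 to 1.00 |

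The last row is an upper bound, because the 33% also covers cross-over, loss to follow-up and other missing data. The documents do not say how many would be reachable withdrawals.

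A simulation of the baseline-adjusted analysis used 30 women in one arm, 10 missing at week 12, SD 2, an assumed baseline to week-12 correlation of 0.5 and 20,000 runs. It gave 0.34, 0.66 and 1.00 for shortfalls of 1, 2 and 3. This confirms that keeping the baselines does not remove the bias; it is not evidence about the size of the shortfall.

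**Comparators**

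- One-arm 95% half-width at n = 20: 2.093 × 2 / √20 = 0.94.
- Between-arm half-width at 20 per arm: 2.024 × 2 × √(2/20) = 1.28.

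**Bias in the difference between arms**

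Equal loss with equal shortfall cancels. As an assumed unequal case, take 14 versus 6 missing of 30 per arm: (14 − 6)/30 × (1 to 3) = 0.27 to 0.80. That split leaves 16 and 24 observed, so its own half-width is 2.024 × 2 × √(1/16 + 1/24) = 1.31.

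**The case against.** **A benign reading exists.** The 7.2.5 list could describe a visit held on the day a woman leaves, when a VSQ would not be the endpoint anyway. The 5.7.2 visit would then be an ordinary Visit 2, VSQ included, and the defect would be a missing cross-reference. This is possible, and it would be wrong to say the protocol forbids the VSQ or that these women certainly lack one. But no passage makes this reading govern, and 7.2.5 is the only list addressed to withdrawn women.

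**Direction and size are inferred.** The adherence sentence in 4.2.1 justifies the choice of endpoint; it does not describe women who leave. They may also leave for adverse events, a newly found exclusion criterion or reasons of their own. The 1 to 3 point range has no source in the documents. Its top value is about 1.7 residual SDs (3/1.73, taking SD 2 and correlation 0.5). Only the extreme case, 1.00, exceeds the 0.94 half-width, and the between-arm case never exceeds its comparator. All of this stands: the size is illustrative.

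**It is a pilot.** Formal comparison is not its focus, and the plan summarizes missing outcomes and tabulates reasons for stopping. Those summaries help interpretation but cannot recover a score that was never requested.

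**Phone collection has a price.** The VSQ is a self-completed form with intimate items. Asking it by phone in an open-label trial may introduce interviewer bias, mainly among women who left. This also stands, and is a reason to prefer the office visit and to record the mode.

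**Conclusion.** The concern holds. Sections 5.7.2, 7.2.4 with the Schedule of Events, and 7.2.5 are not reconciled, and on one natural reading the primary outcome goes uncollected in women who stop early. Confidence in this textual gap is high.

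Confidence in the size is much lower. On the assumed 1 to 3 point shortfall, the bias in an arm mean runs from 0.08 points (5 of 60 unobserved) to 1.00 (20 of 60, the upper bound). The lower end is small against a half-width of 0.94; the upper end matches it. The direction, towards too favourable a result, is plausible but not documented. The number of women affected is unknown: only those withdrawn or terminated, reachable, willing to respond and handled under 7.2.5. The case for changing the plan rests on the fact that a score not requested at week 12 cannot be recovered later, while requesting it costs little.

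**What to change.** - State in 5.7.2 and 7.2.5 that the week-12 VSQ is requested from every randomized woman who agrees, whatever her product use.
- Specify that the 12-week visit in 5.7.2 uses the outcome assessments of 7.2.4, and add a matching note to the Schedule of Events.
- If she will not attend, ask the VSQ during the phone call already planned, timed at week 12, and record the mode of administration.
- State in section 10 that these off-treatment week-12 scores enter the intent-to-treat analysis. Report any VSQ taken before week 12 separately and do not carry it forward.

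The cost is amendment wording, mainly in two sections with short conforming notes elsewhere, and a few minutes at each contact already planned. Some scores will be taken by phone rather than on paper, and women lost to follow-up will still be missing.
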